5.1 If Yes, what procedures are in place to assure safety?

ID: YIEW4E0947A633C00

Name: v2\_Interviews

## Audio or Video Recording/Photographs

You indicated that this study involves audio or video recording/photographing.

1

\* Indicate the type of recording (check all that apply):

- Video
- Audio
- Still Photo
- Other

1.1 If Other, specify:

2

\* What is the purpose of the recording? (i.e., for therapeutic purposes, to establish treatment fidelity, or to establish reliability of assessments)

We will garner feedback on the intervention and the study. Using transcriptions, we will identify themes related to responses in order to optimize the study and the intervention.

3

\* Could the recording be likely to cause discomfort in participants or cause harm if their confidentiality were breached?

- Yes
- No

4

\* How will individuals' identities be protected?

Files with interview questions + notes taken during the interview will only be identified with a participant ID (e.g., FRE01). Audio files will be transferred from the recorder to a UMB-issued (password-protected, HIPAA-compliant) computer within two business days of acquisition, and then will be promptly deleted from the device. Audio files will be transcribed, resulting in de-identified transcriptions of conversations for use in data analysis. Because voices can be identifiable, no audio clips will ever be played in public or in presentations.

ID: V1EW4E094C128C800  
Name: v2\_Audio or Video Recording / Photographs

## Behavioral Intervention

You indicated that this study involves psychosocial or behavioral interventions.

1 \* Describe the intervention (duration, number of sessions, focus, etc.):

Participants will be randomized to one of two arms: TRE or control.

TRE arm: Participants in the TRE arm will be asked to engage in time-restricted eating for 12 weeks. The TRE window is 10 hours long and will be selected by the participant based on their normal meal patterns and preferences. For example, the window could be 7am-5pm, 8:30am-6:30pm, or 12:00pm-10:00pm. However, the window should not change during the intervention period. Every day for the 12 weeks, participants will be encouraged to consume all food and beverages only within the 10-h window; water and medications will be allowable any time and only black coffee and unsweetened tea will be allowable in the mornings before the eating window, as has been done in previous TRE studies to facilitate adherence. Other than black coffee and unsweetened tea in the morning, because of the potential of caffeine and artificial sweeteners to affect circadian rhythm, coffee, tea, chewing gum, and diet beverages will be discouraged during the fasting window.

Control arm: The control arm will be asked to not make drastic changes to their daily routines or lifestyle behaviors. We will emphasize the importance of their participation because we do not know a lot about the relationships between lifestyle routines (e.g., nutrition, physical activity, sleep) and cancer-related fatigue in survivorship. We will ask them to provide feedback on the usability and usefulness of the app for logging these behaviors.

Both arms will be provided with the myCircadianClock app, which allows users to log food intake, exercise patterns, sleep behaviors, and body weight. Through the app, both arms will receive weekly tips for healthy lifestyle behaviors (i.e., diet and nutrition, exercise, sleeping habits, not smoking, see "Additional documents"). For weeks 0, 6, and 12, participants are expected to log food (required) at every eating session, though entries can be made later. For these same weeks, participants are expected to log sleep (recommended, hit "Start Sleep" before bed and then "End Sleep" upon waking). Also, participants can enter whether or not they felt rested (binary). There are other features of the app that participants can use but are not required or even recommended, including logging exercise ("Start" and "End Exercise," type of exercise, intensity) and other health parameters (e.g., vitals, labs). We expect that using the app will take about 5-8 minutes each day.

For weeks that are not data collection weeks, participants have the choice to use the app or not.

ID: VIEW4E0BC12A9F800  
Name: v2\_Behavioral Interventions

## Other Psychosocial or Behavioral Procedures

You indicated that this study involves other psychosocial or behavioral procedures.

1 \* Describe the other psychosocial or behavioral procedures that will be involved in the research:  
Physical activity measurement via actigraphy and measurement of interstitial glucose via continuous glucose monitoring

2 Upload any relevant materials:

Name	Created	Modified Date
------	---------	---------------

There are no items to display

3 \* What is the individual duration of each procedure and what is the entire duration of all procedures?

Both the actigraph and the glucose monitor will be donned at the beginning of the week and can be worn for 7 days straight without charging or actively syncing with a mobile device. Actigraphy and glucose monitoring will occur for 7 days at baseline (week 0), week 6, and week 12 and not weeks 1-5 or 7-11. Actigraphs will be set up in the lab prior to mailing and the participant will not need to do anything except wear it and return it for us to retrieve the data. Continuous glucose monitors will be put on by the participant (or another person of their choice) using instructions provided by the manufacturer. They will hold the reader to the sensor to start collecting data, then do not have to do anything else for the rest of the week. We will ask that they return the reader and sensor with the actigraph the next week, after data collection.

4 \* Are any of the procedures (or do any of the procedures elicit information) likely to cause discomfort in participants or cause harm?

Yes  No

4.1 If Yes, what procedures are in place to assure safety?

The actigraph is a non-invasive device that is worn like a wrist watch. There is a very low potential for causing discomfort (more like annoyance once in a while).

The continuous glucose monitor (CGM) is applied to the back of the arm using an applicator that comes with the device. The CGM includes a filament that inserts about 5 mm into the skin. There is a water-proof adhesive that keeps the monitor in place. There is potential for causing minor, brief discomfort when device is applied and removed. If a participant desires, the back of the arm can be cooled with an ice pack before the glucose monitor is applied. The participant has the option to come on site for help applying and/or removing the device. To reduce discomfort, we will tell participants to avoid hitting it directly or pulling on it (see Study Packet). They can still do all typical activities of daily living, including working out and showering as normal.

ID: VIEW4E0BC6EF1E800  
Name: v2\_Other Psychosocial or Behavioral Procedures

## Data Collection/Record Review

You indicated on the "Type of Research" page that your study involves data collection or record review (i.e., chart review, not self-report).

1 \* What type of data will be collected/analyzed in this study? (Check all that apply)

Retrospective/Secondary Analysis (data has already been collected at the time of initial IRB submission)

Prospective (data is not yet in existence and/or collected)

2 \* Will this study involve adding data to a registry or database for future use?

Yes  No

3 \* Will the data be released to anyone not listed as an investigator on the protocol?

Yes  No

3.1 If Yes, give name(s) & affiliation(s):

ID: V1EW4E0E25A8CA400  
Name: v2\_Data Collection / Record Review

## Prospective Data

You indicated that the study involves the collection of prospective data.

1 \* Where is the data being collected from? (Check all that apply)

- Medical records
- Medical images
- Commercial (for profit) entity
- Publicly available records
- Schools
- Other

1.1 If Other, please specify:

myCircadianClock app, questionnaires, researcher-provided glucose monitor and actigraph, interview, adverse events

2 \* What data fields will you have access to/collect for the study? For example, name, initials, date of birth, Social Security number, income, demographic information, family units, housing, etc.

The Clinical Record form will be completed by study staff from the medical record. The Clinical Record form contains demographics, height, weight, current menopausal status, Karnofsky Performance Status or Eastern Cooperative Oncology Group (ECOG) Performance Status, comorbidities, cancer stage, surgical procedures, types and doses of treatments (e.g., chemotherapy type and dosing, hormone therapy), most recent blood work (e.g., hemoglobin, hematocrit, lymphocytes, etc.), and medical history (e.g., prior myocardial infarction).

myCircadianClock app: diet, sleep, exercise, and health data (We will have access to all that the participant inputs.)

Questionnaires: Please see section 5, Surveys/Questionnaires

Glucose monitor: Interstitial glucose data

Actigraph: Movement data (counts in three axes) and data from the light sensor

Adverse events: patient-reported worsening of symptoms, with special attention to weight loss and severe adverse events (e.g., hospitalization) as defined by the CTCAE v 5.0. Please see section 12, Study Monitoring.

You can also upload a copy of the data fields/variables to be collected for the study:

Name	Created	Modified Date
 Clinical-record.docx(0.01)	2/22/2022 11:32 AM	2/22/2022 11:32 AM

ID: VIEW4E0E25B643800

Name: v2\_Prospective Data

## Clinical Trial Registration

You indicated on the "Type of Research" page that your study is a clinical trial.

1 \* Does the UM Clinical Trials Registry policy require registration of this trial?

Yes  No

2 \* Has this trial been registered?

Yes  No

ID: VIEW4E093BF078C00  
Name: v2\_Clinical Trial Registration

## Clinical Trial Registration Information

You indicated that this clinical trial has been registered.

1 \* Was this trial registered at [www.clinicaltrials.gov](http://www.clinicaltrials.gov)?

Yes  No

2 If no, was this trial registered on a site other than clinicaltrials.gov?

Yes  No

2.1 If Yes, specify the name of the other site:

2.2 Provide justification for registering this trial on this site:

3 \* Registration Number  
NCT05256888

ID: VIEW4E093BF1D0800  
Name: v2\_Clinical Trial Registration Information

## Participant Selection

1 \* How many local potential participants (or specimens/charts) do you anticipate will be screened for this study? **Screening includes determining potential participants' initial eligibility for and/or interest in a study.**  
300

2 \* How many participants (or specimens, or charts) will be enrolled/used for this study? **A local prospective participant is considered enrolled in the study when a UM-approved Informed Consent Document (not including separate screening consent forms) is signed.**

Local - the number being enrolled at this site:

50

Worldwide - the number being enrolled total at all sites (including local enrollment):

50

3 \* Gender:

Male  
 Female

4 \* Age(s):

0 to 27 days (newborn infants)  
 28 days to 12 months (Infant)  
 13 months to 23 months (Toddler)  
 2 to 5 years (Preschool)  
 6 to 11 years (Child)  
 12 to 17 (Adolescents)  
 18 to 88 years (Adult)  
 89 years and older

5 \* Race/Ethnicity:

All Races Included  
 American Indian or Alaskan Native  
 Asian/Other Asian  
 Asian/Vietnamese  
 Black or African American  
 Hispanic or Latino  
 Mixed Race or Ethnicity  
 Native Hawaiian or Pacific Islander  
 White or Caucasian

6

\* Language(s):

English  
 Chinese  
 French  
 Italian  
 Japanese  
 Korean  
 Local Dialect  
 Spanish  
 Vietnamese  
 Other

6.1 Specify Other:

7

\* Are you excluding a specific population, sub-group, or class?

Yes  No

7.1

If Yes, indicate your justification for excluding a specific population, sub-group, class, etc.:

## Vulnerable Populations

1 \* Will you be targeting ANY of the following Vulnerable Populations for enrollment? (Select all that apply)

- Employees or Lab Personnel
- Children (Minors)
- Cognitively Impaired/ Impaired Decision Making Capacity
- Pregnant Women/Fetuses
- Wards of the State
- Students
- Prisoners
- Nonviable Neonates or Neonates of Uncertain Viability
- Economically/Educationally Disadvantaged
- None of the above

Only select populations which you will be targeting for enrollment. Do not include populations that may be enrolled incidentally. Enrollment of a vulnerable population is considered to be "targeted" if the study team will be aware that a subject is from a vulnerable group as a result of interaction with the subject or collection of specific information about the subject, and the research team does not wish to exclude them. "Incidental" enrollment is limited to situations where a study team is unaware that a subject is from a vulnerable group.

ID: VIEW4E0E519917800  
Name: v2\_Vulnerable Populations

## Eligibility

1 \* Do you have an existing Eligibility checklist(s) for this study?  
 Yes  No

1.1 If Yes, upload here. If you need a template, you can download it by clicking [HERE](#). The checklists you upload will also be available under the Documents tab of this application.

Name	Created	Modified Date
------	---------	---------------

There are no items to display

1.2 If No, create an eligibility checklist below:

List inclusion criteria (List each Inclusion Criteria individually, using the ADD button):

### Number Criteria

View 1	Have completed adjuvant chemotherapy, surgery, and/or radiation for cancer, including chemotherapy for hematological neoplasms, at least 2 months and not more than 2 years prior to enrolling. Participants are eligible if they are on maintenance therapy with non-conventional chemotherapy (e.g. targeted therapy)
View 2	Have a baseline level of fatigue, as determined by reporting a score of 4 or higher for the question, "In the last week, how bad was your worst fatigue on a scale from 0-10?"
View 3	Be able to speak and/or read and write in English
View 4	Be at least 18 years old
View 5	Own a smartphone
View 6	Be willing and able to adhere to study procedures, including use of a smartphone app
View 7	Be able to provide informed consent

List exclusion criteria (List each Exclusion Criteria individually, using the ADD button):

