## Lay Summary

1 \* Provide a summary of the background and purpose of the study in language that can be understood by a person without a medical degree.

Cancer-related fatigue affects at least 30-90% of patients with cancer, depending on the type of cancer and their treatment(s) (e.g., chemotherapy, radiation). It is not relieved by sleep or rest, and it sometimes can persist for years after a person's cancer was treated. The fatigue can be so bad that people cannot return to work, hobbies, family roles, or other daily activities, thereby greatly reducing quality of life. The causes of this fatigue are unknown, and we currently do not have anything that can reliably prevent or cure the fatigue. However, there are recent data suggesting that circadian rhythm, or a person's internal body clock, may be disrupted by the cancer experience and contribute to fatigue. Food intake is an external cue that can entrain circadian rhythm. We recently showed that cancer survivors are willing and able to eat all their food within a 10-hour eating window—a practice called time-restricted eating. Herein, we are testing time-restricted eating against a control group to see if time-restricted eating can indeed alleviate cancer-related fatigue.

All participants will be asked to use the myCircadianClock smartphone app to log their food intake and weekly body weight measurements. The app can also be used to log sleep (recommended), exercise (optional), and other health measures (optional). The participants assigned to the time-restricted eating group will be asked to eat all their food in a 10-hour window during the day. People can choose their start time based on their schedule and preferences, but we ask that the window is the same for the whole study (e.g., 7am-5pm, 9:30am-7:30pm). Black coffee and unsweetened tea are allowed before the eating window, and water and medicines are allowed at all times. The participants in the control group will not be restricted to when they can eat. Participants in both groups will give us valuable information regarding how daily behaviors (e.g., diet, physical activity, sleep patterns) are related to the experience of fatigue.

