## Justification, Objective, & Research Design

If you uploaded a separate research protocol document in the 'Research Protocol' page, cite the applicable section and page numbers from that document in the answer boxes below.

1 \* Describe the purpose, specific aims, or objectives of this research. State the hypothesis to be tested:

This pilot randomized controlled trial will test the effects of time-restricted eating vs. an unrestricted eating pattern (i.e., control) on persistent cancer-related fatigue, circadian rhythm, and metabolism. These data build upon a study conducted by [name] (PI) that established the feasibility and safety of time-restricted eating among cancer survivors—cancer survivors were willing and able to eat within a 10-hour window for 14 days. The specific aims are as follows:

Aim 1: To assess the feasibility of time-restricted eating for 12 weeks, utilization of the myCircadianClock app, continuous interstitial glucose monitoring, and the wrist-worn actigraph. We hypothesize that 80% of participants will provide evaluable data regarding their eating window via the app at baseline and 12 weeks. We also hypothesize that at least 80% of participants who are in the time-restricted eating arm and provide evaluable data will eat within a daily average window that is  $\leq 10$  hours.

Aim 2: To estimate the preliminary efficacy of a 12-week time-restricted eating intervention vs. an unrestricted eating pattern on patient-reported fatigue among fatigued cancer survivors, as measured using the Functional Assessment of Chronic Illness Therapy-Fatigue (FACT-F) questionnaire. We hypothesize that FACT-F fatigue subscale scores will be lower for those in the time-restricted eating group compared to the control group at week 12, controlling for baseline levels.

Mechanistic (exploratory) aims: To assess the effects of a 12-week time-restricted eating intervention vs. an unrestricted eating pattern on circadian rhythm (mesor, amplitude, and acrophase from actigraphy), sleep parameters (e.g., sleep efficiency), and biomarkers of metabolism (fasting blood glucose, glucose excursions).

1. To assess cross-sectional associations between circadian rhythms, metabolism, and fatigue at baseline.
2. To explore associations between changes in circadian rhythms, metabolism, and fatigue from baseline to 6 weeks and baseline to 12 weeks.
3. To explore associations between adherence to the intervention and changes in the same measures.

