Aim 1 assesses the feasibility of time-restricted eating over 12 weeks. We will note how many people we can screen; how many we can approach; how many are eligible; how many consent; and what percentage provide evaluable data at baseline and 12 weeks. Using data from myCircadianClock, we will extract how many days the participants ate within a 10-h window and the average length of the eating window at baseline, week 6, and week 12. We will consider a participant "adherent" if they ate within the 10-h window at least 80% of days. This goal is based on prior TRE studies. In regard to retention, it is hypothesized that at least 80% (24 out of 30) of those who provide baseline data also provide data at 12 weeks; this goal is based on colleagues' prior behavioral intervention studies with supportive care outcomes.

Aim 2 aims to provide estimates of efficacy comparing time-restricted eating vs. control on fatigue. Linear mixed models (LMMs) for longitudinal data will be used to assess the intervention effect on continuous outcomes (e.g., fatigue) accounting for correlations between the repeated measures. Generalized Linear Mixed Model (GLMM) analyses will be conducted to assess the effect of the intervention on count outcomes. The fixed effects included in the models will be treatment group (TRE versus control), time (baseline, 6 and 12 weeks), group-by-time interaction term and relevant covariates. Random effects will include individual patients. The hypotheses will be tested by evaluating the interaction term of group and time (i.e., 12 weeks). The results of the analyses together with the mean and SD of FACIT-F values as well as change scores will be used in planning future RCTs. All hypothesis testing will be at the two-sided level of 0.05. Following the intent-to-treat principle, all participants will be analyzed as randomized, regardless of their adherence with the intervention.

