## Recruitment

1 \* Describe plans for recruitment, including the identification of potential participants (or acquisition of charts/records/samples) and initial interactions with them: (If this study involves the VA please list all sites at which recruitment will take place.):

1) Identification

Before recruitment, approval will be obtained by UMGCCC Clinical Research Center (CRC), the University of Maryland School of Nursing (UMSON), and the UMB Institutional Review Board (IRB). The study team will recruit participants using UMSON Department of Pain and Translational Symptom Science established procedures. Potential participants will be identified using three methods: a) screening medical records, b) direct referral from providers (e.g., nurses, nurse navigators, physicians), c) flyers, and (d) advertising via standard UMB- and ICTR-networks (e.g., the Elm).

a) Identification via medical records

Potentially eligible participants receiving care at UMGCCC will be identified in a HIPAA-compliant manner by study personnel via review of scheduled outpatient appointments (via EPIC) with [name], an oncologists on the study team. If other clinician(s) would like to participate in our study, we will add them to the study team and obtain permission to access their clinic schedule(s). Medical records typically show time since completion of adjuvant therapy (e.g., surgery, chemotherapy). If an individual appears to be eligible, the study team will contact the oncologist (or a designee) to notify them of a potential candidate and obtain approval to speak with/contact the patient.

b) Identification via direct referral from clinicians (e.g., physicians, physician assistants, nurses)

The study team is working with several oncologists (including, but not limited to [name]) and their medical teams (e.g., nurses, physician assistants) to identify potential patients at UMGCCC who are likely eligible for our study. If the patient is eligible based on information in the medical records, the provider will be asked to refer the person to the study team, tell the person about the study at their appointment (in person or telehealth), or give them a flyer. The medical team is not expected to field detailed questions related to the study.

c) Flyers

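### The Aim 2 hypothesis conditions on baseline fatigue, but the planned group-by-time test is a change-from-baseline contrast that neither conditions on baseline nor is adjusted by time-fixed covariates entered as main effects

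*Combined protocol and SAP*

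**What the plan says.** - **Hypothesis** (Justification, Objective, & Research Design, Aim 2): fatigue scores in the time-restricted eating group are "compared to the control group at week 12, controlling for baseline levels".
- **Model** (Sample Size and Data Analysis, item 2): a linear mixed model with treatment group, "time (baseline, 6 and 12 weeks"), a "group-by-time interaction term and relevant covariates". For the random part, "Random effects will include individual patients".
- **Test** (same item): "The hypotheses will be tested by evaluating the interaction term of group and time (i.e., 12 weeks").
- **Covariates**: none is named for Aim 2, and the plan does not say whether any interacts with time. Age and depression appear only as example confounders for the exploratory associations.
- **Population** (Eligibility, inclusion criterion 1): treatment finished "at least 2 months and not more than 2 years prior to enrolling", with some maintenance therapy allowed. The Lay Summary says of the fatigue that "it sometimes can persist for years after a person's cancer was treated".
- **Availability** (Recruitment, item 1a): "Medical records typically show time since completion of adjuvant therapy".
- **Allocation and numbers**: allocation is described only as 1:1, and about 25 evaluable participants are expected from 50.

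**The concern.** The hypothesis and the test describe different estimators. Conditioning on baseline compares week 12 scores between people with the same starting score. A group-by-time term with baseline among the outcomes compares mean changes. Both target the same effect under randomisation, but they treat a chance baseline difference differently and do not have the same precision.

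The second consequence is easier to miss. In a change contrast, a covariate that is constant within a person and enters as a main effect shifts all of that person's visits equally and drops out. The covariate clause therefore looks like protection against chance imbalance but gives the tested effect almost none. A result could be reported as covariate-adjusted when it is numerically almost the unadjusted one. The eligibility window of 2 to 24 months makes the question concrete, because fatigue may change over 12 weeks at different rates across that range. The plan says the Aim 2 results will be used in planning later trials.

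**Working it through.** **The plan's own arithmetic.** There is no power calculation to reproduce. From 30 recruited, 10-20% attrition leaves 30 × 0.80 = 24 to 30 × 0.90 = 27, consistent with the stated figure of about 25. The revised figures imply a loss of 1 − 25/50 = 50%.

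**Variance inputs** (the two-week single-arm pilot, research-design section, item 3). The SD of change is 8.1. A mean change of 5.3 with effect size 0.55 implies a score SD of 5.3/0.55 = 9.64; I assume this is the SD of scores, since 5.3/8.1 = 0.65 does not match. With a random intercept:
- residual variance = 8.1²/2 = 32.8
- between-person variance = 9.64² − 32.8 = 60.1
- correlation between visits ρ = 60.1/92.9 = 0.65

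**Step 1: does a main effect adjust the tested term?** Write the outcome as person effect + γx + visit and group terms. The week 12 change is Y12 − Y0, and γx − γx = 0. Simulations with 25 per arm agree:
- Complete data: adding the main effect moved the estimate and its z value by 0 in every run.
- 50% loss by week 12, pilot SDs: mean absolute movement 0.06 to 0.09 points, with essentially no change in sampling SD.
- 50% loss, a separate check with between-person SD 8 and within-person SD 5.7: mean movement 0.07 to 0.21 points, up to 1.2 in single runs.

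**Step 2: which imbalance remains?** Assume months since treatment are uniform on 2 to 24, so the SD is 22/√12 = 6.35 months. The SE of the difference between arms is:
- 25 per arm: 6.35 × √(2/25) = 1.8 months, 95% limits about ±3.5
- 12.5 per arm: 6.35 × √(2/12.5) = 2.5 months, 95% limits about ±5.0

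Now assume that 12-week change varies by 0.2 points per month and force a 4-month imbalance. The expected distortion is 0.2 × 4 = 0.8 points; slopes of 0.1 to 0.4 give 0.4 to 1.6. Mean simulated estimates, true value 0:

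| Data | No covariate | Main effect | Covariate × visit |
|---|---|---|---|
| Complete | 0.75 | 0.75 | 0.07 |
| 50% random loss (simulation error about 0.26) | 0.35 | 0.35 | −0.36 |

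If the covariate affects only the level of fatigue (0.5 points per month, so a 2-point baseline difference at 4 months), the planned contrast averages −0.09 with complete data. That is zero within simulation error of about 0.18: this kind of imbalance is already removed.

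**Step 3: what does conditioning on baseline gain?** With complete data and large samples:

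variance(baseline-adjusted) / variance(change) = (1 − ρ²)/[2(1 − ρ)] = (1 + ρ)/2

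At ρ = 0.65 the SD ratio is √0.824 = 0.91, about 9% smaller. If ρ over 12 weeks were 0.5 or 0.8, it would be √0.75 = 0.87 or √0.90 = 0.95.

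In simulations of 50 randomised, with weeks 6 and 12 as outcomes and both baseline and the covariate as main-effect predictors, the sampling SD fell relative to the planned model by:
- about 8% (complete data) and 4% (50% loss) when the covariate is unrelated to change
- up to about 17% (complete data) and 12% (50% loss) at an assumed 4 points of week 12 change per covariate SD

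**Step 4: are the two estimators interchangeable?** No. If the arms differ by d at baseline, the change contrast subtracts d and the baseline-adjusted one subtracts ρd, so they differ by (1 − ρ)d. With 12.5 per arm, d has SE 9.64 × √(2/12.5) = 3.86, so the gap has an SD of 0.35 × 3.86, about 1.4 points.

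**The case against.** The strongest reply is that nothing here is invalid. The planned contrast is unbiased under randomisation, chance imbalance is already in its standard error, and this is a pilot with no power claim. Including baseline as a visit is also, loosely, a way of controlling for it. All of that stands; the case rests on precision and on agreement between hypothesis and test.

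Three stronger readings are tempting, and the documents do not support them.

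- **That the plan enters covariates only as main effects, so they can never affect the test.** The form is not stated; main effects are inferred from a list whose only interaction is group-by-time. The cancellation is exact only for complete data with a random intercept. It would hold in the complete-case analysis that the Missing data section allows, but with all available visits the estimate moves slightly.
- **That any imbalance in time since treatment stays in the estimate as bias.** Only the part that predicts change stays, as chance error; selective dropout could make it systematic, but nothing in the documents shows that. Nor do they say how change varies with months since treatment, so every slope used here is assumed.
- **That covariate-by-visit terms are an equivalent remedy.** They give a different estimate and are a trade-off. They widened the sampling SD by about 2% at slopes of 0 to 1 point per covariate SD and helped only from about 2. The illustrative 0.2 points per month is 0.2 × 6.35 = 1.3 points per SD, below that level.

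**Conclusion.** The point holds as a mismatch between hypothesis and test, with a modest but avoidable cost. The planned test does not condition on baseline FACIT-F, and time-fixed covariates in their most natural form do essentially nothing to it. Conditioning on baseline would cut the sampling SD by roughly 4% to 8% even with an uninformative covariate, and by about 12% (50% loss) to 17% (complete data) at the steepest slope tried. These figures rest on a two-week single-arm pilot's SDs, a random-intercept structure and loss unrelated to outcome; the gain is smaller if scores correlate more strongly over 12 weeks and larger if less. Time since treatment is a sensible example of a covariate, but its relation to change is not established.

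**What to change.** In Sample Size and Data Analysis, item 2, replace the Aim 2 model by one along these lines: FACIT-F fatigue at weeks 6 and 12 are the outcomes; fixed effects are baseline FACIT-F fatigue, group, visit and group-by-visit; patient is a random effect; the test is the group difference at week 12. List any further covariates in advance and enter them as main effects, which now adjust the contrast. Time since completion of treatment is an optional choice and is already checked for eligibility; with about 25 evaluable participants the list should be short. Report the estimate without further covariates alongside.

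The cost is a few sentences and no new data. The real downside is that participants with no post-baseline visit contribute nothing unless imputed, which matters at 50% loss. The multiple imputation already described under Missing data can cover them, and the text should say that it applies to this model. Under a complete-case analysis those participants are excluded anyway.
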